4.5.2 Guidance for Appendectomy in Patients Randomized to Antibiotics

For participants randomized to the antibiotics arm, appendectomy will be recommended when there is:

- 1. Development of diffuse peritonitis;
- 2. Development of severe sepsis/septic shock (e.g., new presumed sepsis-related organ dysfunction, elevated lactate, and/or fluid unresponsive hypotension)and/or
- 3. Worsening signs and symptoms of appendicitis after 48 hours following the first antibiotics dose.

Absent these criteria, patients will be encouraged to continue with the antibiotics treatment strategy, especially during the first 48 hours of treatment. At any point after initiating the antibiotics strategy, the surgeon and patient can determine that an appendectomy should be performed. When a decision for appendectomy is being considered, the site lead investigator will be notified to determine if any of the above criteria are met or, if not, to review the surgeon's and patient's specific reasons for recommending (surgeon) or requesting (patient) appendectomy. These reasons will be recorded for analysis and reviewed by the project manager. If the project manager believes an appendectomy was recommended by the surgeon outside of the protocol, it will be reviewed by a clinician not otherwise affiliated with the study who will follow up with the site PI. All appendectomies performed outside of study protocol, other than those requested by the participant, will be reported as protocol violations.

All participants will be encouraged to return to the hospital or clinic site if they have recurrent signs and symptoms of appendicitis after the four-week assessment and encouraged to undergo repeat diagnostic imaging to detect recurrent appendicitis. Participants in the antibiotics arm who return to any of the study sites during the follow-up period (but after the four-week assessment) with recurrent appendicitis will be offered appendectomy or the option of another attempt at antibiotics but will not be re-randomized or moved to another cohort.

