11.3 Protocol Violations and Deviations

A protocol violation is any non-compliance with the clinical trial protocol or Good Clinical Practices. The noncompliance may be either on the part of the participant, the investigator, or the study site staff and most often is related to study enrollment. Anticipated protocol violations are 1) Participant enrolled but did not meet inclusion criteria, 2) Participant enrolled but exclusion criteria present or eligibility criteria not met, 3) Consent not obtained in accordance with IRB guidelines, 4) Randomization failure, 5) Clinical team intervention outside of the protocol (other than those elected by participant), 6) Participant in antibiotics arm received antibiotics outside of protocol during hospital stay, and 7) Participant in antibiotics arm received antibiotics outside of protocol at discharge. Participants enrolled and later found to be ineligible will still be followed. Specifically, a participant enrolled into the randomization or observational cohort that is later found to not have appendicitis will still be asked to complete study assessments. To document the participant's ineligibility, a protocol violation will be submitted. Participants enrolled in the EMR cohort who are later found not to have appendicitis will be withdrawn from the study. As a result of violations, corrective actions will be developed by the site and implemented promptly.

A protocol deviation is a smaller digression from study protocol. Deviations are monitored with consideration for protocol amendment should it become clear that the original protocol was too inflexible. The only anticipated protocol deviations are >7 hours between first administration of antibiotics and study approach by the research coordinator and not watching the video or reviewing the study pamphlet prior to study consent. Additional protocol deviations will be recorded and described.

It is the responsibility of the site to use continuous vigilance to identify and report violations and deviations within 5 working days of identification of the protocol violation/deviation.

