While crossovers are anticipated, the ITT approach is an appropriate primary analysis. We will conduct a secondary as-treated analysis of the primary outcome measure that appropriately accounts for patient- or provider-level characteristics found to be differentially represented among patients who crossover and patients in the antibiotics arm who are treated with appendectomy. Careful as-treated and secondary data analyses are of elevated importance towards understanding the effectiveness of the treatments and in assessing for whom antibiotics-first is an appropriate treatment.⁹ A simple as-treated analysis is problematic because randomization is broken when select patients in the antibiotics and do not undergo appendectomy. Thus, patients who are successfully treated with antibiotics and do not undergo appendectomy may differ demographically or clinically in ways that introduce bias in a naive as-treated analysis. Detry (JAMA 2014) recommends both an ITT and a careful per-protocol analysis to address treatment changes in non-inferiority trials where non-adherence, crossover, or treatment changes are present. If we find a difference between the ITT and as-treated results, the ITT results will be considered the primary analysis.¹⁰

Per-Protocol Analysis: It is important to consider subjects who do not follow the protocol since these individuals bias treatment group comparisons toward no difference, but this is the alternative hypothesis rather than the null hypothesis for non-inferiority trials. Therefore, it is recommended that an ITT analysis is augmented with a per-protocol analysis that considers only those subjects from both treatment groups who adhered to the protocol. Although such a subset analysis may have bias due to patient factors associated

with non-adherence to the protocol it is a valuable companion analysis that does not suffer from nonadherence bias in the way that ITT analysis may. Our protocol states the conditions that are considered to adhere to the protocol, therefore we use the following criteria:

- All patients: exclude not randomized in accordance to the protocol (i.e., meets all inclusion/exclusion criteria, randomization assignment followed)
- Surgical group: exclude subjects whose randomization assignment was ignored.

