- Antibiotics group: exclude subjects whose randomization assignments were ignored, were not given protocol-described antibiotics, or who underwent an appendectomy (for non-protocol indications, as described by sites).

For the antibiotics group we have a direct measurement of whether eventual surgery is compliant with the protocol as reported by the sites. In the per-protocol analysis we will exclude subjects according to the criterion above, and then analyze EQ5D using mean differences and the associated confidence interval to judge non-inferiority similar to our ITT analysis plan.

As-Treated Analysis: We will consider a two-stage approach for this as-treated analysis: 1) To identify subgroups that are likely to require appendectomy and therefore should not be considered as good candidates for treatment with antibiotics-first, and 2) To estimate the complier average causal effect (CACE), which seeks to compare the outcomes of patients treated successfully in the antibiotics-first arm (i.e., did not ultimately have surgery) with patients randomized to the appendectomy arm who similarly would not have crossed over **had they been randomized to the antibiotics-first arm**. The CACE framework considers the ITT mean in each randomized arm as being comprised of two subgroup means: patients who would be successfully treated with antibiotics-first without appendectomy, and patients who would eventually require appendectomy after being treated with antibiotics-first. We are able to directly observe which patients in the antibiotics-first arm ultimately cross over, but require the CACE framework to identify similar patients in the appendectomy arm. We will use a maximum likelihood mixture modeling approach to identify the optimal comparison group from the control arm for observed compliers in the intervention arm.¹¹ This application of mixture modeling permits an examination of two aspects of intervention process, the prediction of early antibiotics failures in the appendectomy-first group and the examination the treatment effect on quality of life among patients who are suitable candidates for treatment with antibiotics first.¹²

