Analysis of Secondary Patient-Reported Outcomes: We will also compare secondary patient reported outcomes (i.e., 10 PROMIS Global Health Short Form, GIQLI, and the Decision Regret Scale) using an ITT framework and linear regression models. Similar to the primary outcome measure, secondary patient-reported outcomes will be assessed using model-based point estimates and associated confidence intervals. The magnitude of effect will be judged a posteriori using margins that are of comparable magnitude as the EQ-5D in terms of the Cohen's d statistic. In an exploratory analysis, the complete longitudinal trajectory of all PRO metrics will be assessed with linear mixed effects models.

Exploratory Aim A Analysis Plan: Using only data from patients enrolled in the antibiotics-first arm, we will also examine the association of these characteristics with eventual appendectomy. The primary analysis will consider appendectomies performed for any reason. A secondary analysis will define appendectomies as those performed for: (1) acute clinical reason 0-30 days post randomization, (2) non-acute clinical reason and (3) recurrence after a period of symptom resolution (30+ days post randomization).

We will employ univariate logistic regression models to identify and characterize associations with unplanned appendectomy. If we find that a number of baseline characteristics are relevant and the rate of unplanned appendectomy is high enough (e.g., >10-15%), we will use multivariable analyses to compare these characteristics among those undergoing early appendectomy (defined within the first 30 days) and eventual appendectomy (4 weeks to 2 years). Due to the potentially large number of input variables, interactions, and longitudinal assessments we will also use modern model development methods such as the LASSO with boosting.^{13,14} Boosting provides a more sophisticated approach towards building multivariable

predictive models and allows nonlinear relationships between the input variables and risk of requiring appendectomy after first being treated with antibiotics. Boosting is a multiple prediction and aggregation method for classification, where a "base learner" fitting method is fitted multiple times on reweighted data and a final estimator is constructed through a linear combination of the multiple estimates. Results of these analyses will be considered hypothesis generating and may support secondary studies aimed at predictive modeling.

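### The per-protocol set for the week-4 EQ-5D puts no time limit on excluding appendectomies, so surgery after the outcome can remove patients, in the antibiotics arm only

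*SAP*

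**What the plan says.** The primary outcome is the EQ-5D at 4 weeks (final SAP, Outcome Measures). The final SAP adds a per-protocol analysis of that outcome and ties its criteria to the protocol: "Our protocol states the conditions that are considered to adhere to the protocol, therefore we use the following criteria".

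- **Both arms:** patients not randomized in line with the protocol are excluded.
- **Appendectomy arm:** "Surgical group: exclude subjects whose randomization assignment was ignored".
- **Antibiotics arm:** patients are excluded if their assignment was ignored, if they were not given antibiotics described in the protocol, or if they were patients "who underwent an appendectomy (for non-protocol indications, as described by sites".

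The SAP then explains how the last criterion is measured: "For the antibiotics group we have a direct measurement of whether eventual surgery is compliant with the protocol as reported by the sites". It states no time window. Under Exploratory Aim A Analysis Plan, the same document uses the word for a period that begins after the primary outcome: "eventual appendectomy (4 weeks to 2 years".

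On participant requests, Protocol 4.5.2 says: "All appendectomies performed outside of study protocol, other than those requested by the participant, will be reported as protocol violations". Protocol 11.3 lists as an anticipated violation: "Clinical team intervention outside of the protocol (other than those elected by participant". The per-protocol criteria do not mention requests.

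**The concern.** A per-protocol set for a week-4 outcome should depend only on what happened up to the week-4 measurement. Surgery in month 6 cannot be non-adherence that affected an EQ-5D score completed in week 4. If it removes the patient, the analysis selects on the future. Set membership would also depend on how long each patient had been followed when the data were cut.

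The selection works in one arm only. If the patients who later have non-protocol surgery were already scoring lower at week 4, removing them raises the antibiotics mean and helps a non-inferiority claim. The SAP adds the per-protocol analysis because non-adherence can make an ITT comparison look falsely similar, and it uses the resulting confidence interval to judge non-inferiority. A safeguard that can itself lean towards non-inferiority is weaker than intended.

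A second gap sits beside the first. Two statisticians could class participant-requested appendectomies differently and so build different per-protocol sets from the same data.

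**Working it through.** **1. Does the rule reach past week 4?** The criterion has no window, and the explanatory sentence refers to eventual surgery, which the SAP elsewhere runs from 4 weeks to 2 years. Protocol 2.1 gives follow-up of up to two years. The protocol also expects late surgery for reasons other than recurrence: section 5.2.3 records whether an appendectomy was for recurrence or was elective/interval, and section 6.2.2 lists planned or elective appendectomy. That late exclusions are intended is an inference from the missing limit, but nothing in the text prevents them.

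**2. The arms side by side.** The appendectomy-arm criteria concern eligibility, randomization and whether the assignment was followed. None depends on an event after the initial treatment. In the antibiotics arm, an appendectomy during follow-up is itself a criterion.

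**3. The plan's own figure.** The plan gives no figure for the per-protocol set. The number analysed comes from the sample size in Protocol 8.5: mean 0.90, SD 0.12, one-sided α 0.025, 80% power at a 3% difference, 90% follow-up. Reading 5% and 3% relative to the mean gives 0.045 and 0.027, a distance of 0.018.

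- Per arm: 2 × 0.12² × (1.960 + 0.842)² / 0.018² = 698, so 1396 in total.
- 1396 / 0.90 = 1552, as stated.
- The absolute reading (0.05 and 0.03) gives 1132, or 1258 after loss to follow-up, which does not match.

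The number analysed per arm is 1552 × 0.90 / 2 = 698.4. The result below does not depend on which reading of the margin is used.

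**4. Shift in the mean.** Let p be the share of the antibiotics arm excluded for surgery after week 4. Let the remaining patients have week-4 mean m and the excluded patients m − d. The full-arm mean is (1 − p)m + p(m − d) = m − p·d. After exclusion it is m. The shift is p·d.

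**5. Illustration.** The documents give neither p nor d, so the values below are assumptions. SE = 0.12 × √(1/698.4 + 1/[698.4(1 − p)]). If the true difference sits exactly at the margin, the chance that this analysis declares non-inferiority is Φ(p·d/SE − 1.96).

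| p | d | antibiotics n | shift p·d | SE | one-sided error |
|---|---|---|---|---|---|
| any | 0 | – | 0 | – | 0.025 |
| 2% | 0.05 | 684 | 0.001 | 0.00645 | 0.036 |
| 5% | 0.05 | 663 | 0.0025 | 0.00651 | 0.058 |
| 10% | 0.05 | 629 | 0.005 | 0.00660 | 0.115 |
| 10% | 0.10 | 629 | 0.010 | 0.00660 | 0.328 |

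Against a margin of 0.05, shifts of 0.001 to 0.005 are 2% to 10%. A ceiling on p comes from Protocol 2.0: in earlier trials nearly 3 in 4 antibiotics patients avoided surgery in the first year, so about 25% had surgery for any reason. The share that is both non-protocol and after week 4 must be smaller.

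**6. Participant requests.** Protocol 4.5.2 lists three findings for which surgery is recommended, lets surgeon and patient choose surgery at any point, and exempts requested surgery from violation reporting. Protocol 11.3 repeats the exemption. The final SAP's Study Design section counts choosing appendectomy after antibiotics have started as crossover and refers the reader to the per-protocol definition, which excludes by indication and does not say whether a request is one. The classing is therefore open.

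**The case against.** The strongest reply is that the ITT analysis is primary and the per-protocol analysis is openly a companion. The SAP concedes it may be biased by factors linked to non-adherence, and as-treated and CACE analyses also address treatment change. That limits the consequences. It does not supply a time window, and a general caveat about adherence does not cover exclusion on events after the outcome. The SAP says ITT prevails over as-treated results but gives no rule for disagreement between ITT and per-protocol.

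Several stronger readings are tempting and are not supported:

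- **That the SAP contradicts the protocol on participant requests.** The SAP never mentions requests. The sentence in Protocol 4.5.2 can be read as placing them outside protocol but exempt from reporting, and being reportable is not the same as adhering to the assigned strategy. This is an ambiguity.
- **That surgery for recurrence after week 4 would be excluded.** Protocol 4.5.2 says patients with recurrence after the four-week assessment will be offered appendectomy, so such surgery is not plainly non-protocol. Late exclusions would mainly be elective, interval or otherwise non-indicated cases.
- **That the bias is known to favour antibiotics.** Patients with peritonitis, severe sepsis or worsening after 48 hours meet the protocol's criteria and stay in the set. Nothing in the documents shows that those excluded score lower at week 4.
- **That site classification is improper and the independent clinician should decide.** Protocol 4.5.2 has the site lead investigator determine whether the criteria are met. The outside clinician sees only surgeon-recommended cases flagged by the project manager, so that review cannot classify every appendectomy.

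**Conclusion.** The concern holds for the missing time limit. As written, surgery after the week-4 EQ-5D can remove a recorded outcome, and only in the antibiotics arm. This can bias the companion non-inferiority analysis, towards antibiotics if the excluded patients score lower at week 4 and against them if they score higher.

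The size cannot be determined from the documents. For an assumed p of 2% to 10% and d of 0.05 the shift is 0.001 to 0.005, and one-sided error at the margin for this analysis moves from 0.025 to between 0.036 and 0.115. With d = 0 there is no effect. These figures assume SD 0.12 and 698.4 analysed per arm before exclusion. They do not apply to the primary ITT test.

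On participant requests, the supported conclusion is only that their class is undefined and must be reconciled across the two documents. Whether they belong in the main per-protocol set is a trade-off: keeping them retains crossovers, which the SAP says pull the comparison towards no difference, while dropping them selects on a post-randomization choice.

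**What to change.** In the final SAP's Per-Protocol Analysis:

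1. Count an appendectomy as a per-protocol exclusion only if it was performed before the patient's own week-4 EQ-5D date. If that EQ-5D is missing, use the close of the assessment window (day 56, Protocol 5.2.4).
2. State how participant-requested appendectomies are classed, reconciled with Protocol 4.5.2 and 11.3 and with the crossover definition in the SAP's Study Design section. Report the per-protocol result both with and without these patients. Which of the two is main is for the trial team to decide and state in advance.

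The cost is SAP wording and one extra run. Reasons for surgery are already recorded (Protocol 4.5.2, and the Appendectomy Form in 5.3), and the SAP already needs surgery dates for its 0–30 and 30+ day categories under Exploratory Aim A. The primary ITT analysis does not change.

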We will consider a two-stage approach for this as-treated analysis to: 1) identify subgroups that are likely to require appendectomy, therefore, should not be considered as good candidates for treatment with antibiotics, and 2) estimate the complier average causal effect (CACE), which seeks to compare the outcomes of patients treated successfully in the antibiotics arm (i.e., did not ultimately have surgery) with patients randomized to the appendectomy arm who similarly would not have crossed over had they been randomized to the antibiotics arm. The CACE framework considers the ITT mean in each randomized arm as being comprised of two subgroup means: 1) patients who would be successfully treated with antibiotics without appendectomy and 2) patients who would eventually require appendectomy after being treated with antibiotics. We are able to directly observe which patients in the antibiotics arm ultimately cross over, but require the CACE framework to identify similar patients in the appendectomy arm. We will use a maximum likelihood mixture modeling approach to identify the optimal comparison group from the control arm for observed compliers in the intervention arm.³³ This application of mixture modeling permits an examination of two aspects of intervention process, the prediction of early antibiotics failures in the appendectomy group and the examination the treatment effect on QoL among patients who are suitable candidates for treatment with antibiotics.34,35

We will also compare secondary PROs (i.e., 10 PROMIS Global Health Short Form, GIQLI, and the Decision Regret Scale) using an ITT framework and linear regression models. Similar to the primary outcome measure, secondary PROs will be assessed using model-based point estimates and associated confidence intervals. The magnitude of effect will be judged a *posteriori* using margins that are of comparable magnitude as the EQ-5D in terms of the Cohen's d statistic. In an exploratory analysis, the complete longitudinal trajectory of all PRO metrics will be assessed with linear mixed effects models.

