8.5 Sample Size and Statistical Power

Prior studies suggest that non-clinical outcomes (e.g., loss of time from work and pain scores) were similar between groups, but did not evaluate a global QoL measure. The EQ-5D QoL

index ranges from 0 (worst QoL) to 1 (highest QoL), where anchor-based methods have shown that the MCID ranges 5%-10%. Based on data from a prior study of appendectomy with EQ-5D scores at 12 weeks, we estimate that the mean EQ-5D for appendectomy patients will be 0.90 with a standard deviation of 0.12. In order to assess QoL differences between interventions, we will recruit a total of 1552 patients assuming a 90% follow-up at four-weeks. This gives the study high power (>99%) to rule out EQ-5D differences between-groups as small as 5% (e.g., if we observe treatment differences of 0 to 2%) and 80% power if we observe a treatment difference of 3% (Table 5, below).

Previous Washington State evaluations of patients undergoing appendectomy (Table 1). identified that 2-3% of the population is African American, 10-12% Hispanic, 10-15% are Medicaid beneficiaries, and 10% will be above 64 years of age. Recruiting 1552 total patients will allow for a subgroup evaluation based on older age and Medicaid beneficiary status. Assuming 50% recruitment of these populations we anticipate including ~500 Medicaid beneficiaries and ~450 patients ≥65 years. As demonstrated in Table 5, this study also has adequate power (>80%) to rule out differences of 5% for observed treatment effect of Δ =0% within subgroups as small as n=250 patients, or treatment differences of Δ =-1% within subgroups of at least n=400. For this reason, we expect the study will be able to assess these two subgroups. All other subgroup evaluations will be post hoc and used for hypothesis development only.

Table 5. Statistical Power to Declare Non-inferiority on Patient-reported QoL, Overall and by

Subgroup (Non-inferiority Margin, M = -5%, one-sided α =0.025).

Treatment Difference A	Overall		Subgroups	
Treatment Difference, Δ	N=1552	N=250	N=400	N=500
-3%	82.6%	-	-	-
-2%	99.4%	-	57.1%	67.9%
-1%	100%	62.4%	83.8%	91.4%
0%	100%	83.0%	96.4%	98.8%

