General Analytic Strategy: The primary evaluation of EQ-5Dat 4 weeks will be conducted using an intention-to-treat (ITT) analysis, where patient data areanalyzed according to the patient's randomized treatment assignment. Using this analytic approach in a non-inferiority study design comparing antibiotics-first treatment to appendectomy, we aim to test whether the global EQ-5D scores are not different by more than a margin of 5% (M = 5%). The margin (5%) was selected because it is within the meaningful clinical

important difference (MCID) threshold of the EQ-5D, which is 5-10%¹⁻³.

Primary Analysis. Aim 1: Patient-reported QoL, as measured by the EQ-5D at 4 weeks, will be assessed using a linear regression model that adjusts for an indicator of randomized treatment group assignment and for all factors used to stratify randomization (i.e., practice site and appendicolith). As recommended by the United States Food and Drug Administration guidelines on clinical trial design⁴, the estimated treatment effect and 97.5% one-sided confidence interval (CI) will be compared to the non-inferiority margin (M = -5%)⁵⁻⁷. We will conclude that antibiotics are non-inferior to appendectomy when the entire 97.5% one-sided confidence interval is greater than M, as in example scenario A (Figure 1). This is equivalent to a one-sided (alpha=0.025) test of the null hypothesis H₀: $\Delta \leq -5\%$, where Δ represents the difference in mean EQ-5D at 4-weeks comparing antibiotics-first to appendectomy-first. If the null hypothesis of H₀: $\Delta \leq -5\%$ is rejected at Figure 1. Example trial conclusions in a non-inferiority trial.

the final evaluation, we will then conduct a test of superiority to determine the level of statistical evidence supporting an alternative hypothesis $H_A: \Delta > 0\%$ (i.e., scenario B of Figure 1). For Sub Aim 1, we will similarly evaluate non-inferiority on patient-reported QoL among the cohort *with and without* appendicolith. Patients whose randomization was

performed for the incorrect appendicolith group (e.g., research coordinator selected the wrong button during randomization) will be assigned to the group representing their true status.

Aim 1 Secondary Analyses: Secondary analyses of the primary outcome measures will include examining the entire trajectory of EQ-5D QoL measurements for each patient using statistical methods for longitudinal data such as linear mixed effects models or generalized estimating equations (GEE).⁸

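### The standardised margin for judging the secondary PROs is tied to the EQ-5D, but its value, SD and time point are not fixed before the results are seen

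*SAP*

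**What the plan says.** The rule is in the final SAP, under Analysis of Secondary Patient-Reported Outcomes. It covers the "10 PROMIS Global Health Short Form, GIQLI, and the Decision Regret Scale". These are compared by randomised arm with linear regression and reported, like the primary outcome, as point estimates with confidence intervals. The SAP then says: "The magnitude of effect will be judged a posteriori using margins that are of comparable magnitude as the EQ-5D", with the comparison made "in terms of the Cohen's d statistic". Protocol section 8.3 (Secondary Analysis, Aim 1) has the same rule: "using margins that are of comparable magnitude as the EQ-5D in terms of the Cohen's d statistic".

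Neither text gives a value of d, the SD on which it rests, a time point or a margin in scale points. No SD for any of the three instruments appears in either document.

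Four other places bear on the point:

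- The EQ-5D margin is fixed in advance at 5%, and section 8.5 gives planning values: "we estimate that the mean EQ-5D for appendectomy patients will be 0.90 with a standard deviation of 0.12". Those values come from a prior study with scores at 12 weeks; the primary endpoint is at four weeks.
- Analysts know the allocation (protocol section 8.1; final SAP, Study Design and Treatment Allocation).
- The margins based on MCIDs in the SAP's Aim 2 plan apply to clinical endpoints, not to these PROs.
- Aim 1 and the central hypothesis (protocol section 3.1) speak of PROs in general, and section 6.1, on the primary outcome, lists all of these instruments in Table 4.

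**The concern.** A margin protects a non-inferiority judgement only if it is settled before anyone can see which value gives the preferred answer. Here the anchor is stated but the number is not, and the judgement is made afterwards by people who know the arms. Five choices stay open:

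- which EQ-5D SD is used to form d: planned or observed, pooled or control arm;
- whether 5% is 0.05 on the 0 to 1 index or 5% of the mean;
- which SD turns d into points on each secondary instrument;
- which visit is judged, since all three instruments are collected at week 4 and again later (Table 2);
- how close to the EQ-5D's d a margin must be to count as comparable.

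Two smaller gaps add to this. Higher Decision Regret scores are worse, opposite to the EQ-5D, and PROMIS Global Health yields two component scores (Table 4). The SAP addresses neither.

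At stake are statements that antibiotics are no worse than surgery on gastrointestinal quality of life, general health or regret. Such statements would naturally be read as part of the answer to Aim 1.

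**Working it through.** **The plan's own figure.** The documents give none for the secondary margins. The nearest is the EQ-5D power in Table 5 (82.6% at a difference of -3%). From its labelled inputs, the standard error is 0.12 × √(2/698.4) = 0.00642 and the power is Φ(0.02/0.00642 − 1.96) = 87.6%, so that cell does not reproduce. The difference is conservative, and nothing below depends on it.

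**Inputs**

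- Margin 5%: 0.05 if absolute, or 0.05 × 0.90 = 0.045 if relative to the planned mean (final SAP, General Analytic Strategy; protocol 8.5).
- Planned EQ-5D SD 0.12 (protocol 8.5).
- N = 1552, 90% follow-up, equal allocation: 1552 × 0.9/2 = 698.4 per arm.
- One-sided alpha 0.025, so z = 1.96.
- Assumed: week-4 EQ-5D SDs of 0.10 and 0.15; GIQLI SD of 20 points; the same 90% follow-up for the secondary PROs; no gain in precision from covariates.

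**Step 1, the margin as d.** d = margin/SD.

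**Step 2, the CI half-width in SD units.** 1.96 × √(2/698.4) = 0.105.

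**Step 3, the largest observed deficit that still passes.** d − 0.105.

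**Step 4, illustration in points.** d × 20 on the GIQLI (range 0 to 144).

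| Reading | d | Largest passing deficit (SD) | GIQLI margin (points, SD 20 assumed) |
|---|---|---|---|
| 0.05/0.15 (assumed SD) | 0.333 | 0.228 | 6.7 |
| 0.045/0.12 (5% of 0.90) | 0.375 | 0.270 | 7.5 |
| 0.05/0.12 (planning values) | 0.417 | 0.312 | 8.3 |
| 0.05/0.10 (assumed SD) | 0.50 | 0.395 | 10.0 |

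At the planning d, an assumed GIQLI SD of 15 to 25 points gives margins of 0.417 × 15 = 6.3 to 0.417 × 25 = 10.4 points.

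**Step 5, can a verdict change?** Take an observed deficit of 0.30 SD. The lower confidence limit is −0.30 − 0.105 = −0.405. That clears −0.417 but not −0.375 or −0.333. The first two of these thresholds use the same planned SD and differ only in how 5% is read, so the verdict can change without any observed EQ-5D SD being used.

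**Step 6, how much is sampling noise?** The relative standard error of a pooled SD from about 1397 patients is 1/√(2 × 1395) = 1.9%. If the true SD is 0.12, two standard errors move d only between 0.05/(0.12 × 1.038) = 0.40 and 0.05/(0.12 × 0.962) = 0.43. Wider movement needs a real departure from 0.12 or a different convention.

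**The case against.** The strongest reply is that the sentence does not leave the margins free. The words *a posteriori* can be taken to describe when the effect is judged, while the margins are tied to a reference written down beforehand. The EQ-5D margin and planning SD are both in the documents, so d of about 0.42 can be derived today. The SAP also sets no hypothesis or alpha for these outcomes, whereas for the primary it states: "This is equivalent to a one-sided (alpha=0.025) test of the null hypothesis". Readers who see the estimates and CIs can apply their own threshold.

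Much of this stands. A reader might infer that the margins will be computed from the EQ-5D SD observed in the trial, or that claims can be made or withheld at will. The documents do not support either. No passage names the observed SD, the requirement of a comparable d limits the choice, and sampling error in the SD is small. In points the margin is 0.05 × SD(instrument)/SD(EQ-5D), so if a more variable sample raises both SDs, the changes partly cancel.

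It does not close the gap. The derivable d is nowhere stated, has two readings (0.417 and 0.375), and still needs an SD for each instrument that the documents do not supply. Nor is this plainly descriptive reporting: the text speaks of margins, likens the assessment to the primary one, and sits under a central hypothesis of PRO non-inferiority.

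**Conclusion.** The concern holds in a limited form: the rule is anchored but incomplete, and what is missing can decide a verdict. Between d = 0.333 and d = 0.417, observed deficits of roughly 0.23 to 0.31 SD pass or fail according to the d used. Between the two readings of the planning values alone, the window is 0.27 to 0.31 SD. Deficits below about 0.23 SD pass at every value in the range 0.333 to 0.417.

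The 0.417 and 0.375 rest on the plan's own figures; the 0.333 and 0.50 rest on assumed week-4 SDs. All the windows assume about 698 patients per arm with data.

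It would be wrong to extend this to the trial's main result. The EQ-5D margin, test and alpha are fixed in advance, and that conclusion is untouched.

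**What to change.** Delete *a posteriori* from the sentence and record the following in the SAP before secondary PRO results by arm are examined:

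- a standardised margin of d = 0.42, stated as 0.05 absolute divided by the 0.12 of protocol section 8.5, applied at week 4;
- each instrument standardised by its own pooled week-4 SD, computed without arm labels;
- the sign reversed for the Decision Regret Scale;
- the margin applied to both PROMIS component scores;
- other time points reported as estimates and CIs only.

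The scale-point margin would still depend on trial data, but through a quantity fixed by rule and calculated without reference to arm. Because the DSMB reviews PROs during the trial (section 8.6), the SD and margins should be recorded by staff who have not seen secondary PRO results by arm.

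The alternative is to report all secondary PROs as estimates with CIs and to say that no non-inferiority statement will be made.

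The cost is a short SAP amendment and the loss of post hoc flexibility. No data or patients are needed. With power = Φ((0.417 − true deficit)/√(2/698.4) − 1.96), the planned size gives 98.2% at a true deficit of 0.2 SD and 59.0% at 0.3 SD.
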